7.4.3 Analyses of Secondary Endpoints

7.4.3.1 Analyses of Secondary Mucosal Secretory Immunogenicity (S-IgA) Endpoints

Descriptive statistics (GMT, GMFR, seroconversion) for mucosal S-IgA against WCE, PT, FHA, PRN, and any other anti-pertussis mucosal antibodies identified during assay development will be presented at each time point and by treatment group.

Comparisons between two time points (eg, Day 29 and baseline) will be conducted using a paired t-test as outlined in Section 7.4.1.1. Non-interference or non-inferiority comparisons between two treatment groups (eg, BPZE1 + Boostrix being non-inferior to Boostrix by GMT at Day 29) will be conducted using a two-sample t-test as outlined in Section 7.4.2. Non-inferiority comparisons between two proportions will be conducted using the Agresti-Caffo method as outlined in Section 7.4.2.

Analysis of covariance (ANCOVA) model will be used to examine the effects of age or other baseline demographics on differential responses to induction of mucosal S-IgA immunity.

Subgroup analyses by age (6 to 10 years and 11 to 17 years, inclusive), time since last aP vaccination (prior to study entry), or other baseline demographics and by baseline antibody level (by quantile) will be conducted for BPZE1, BPZE1 + Boostrix, and Boostrix treatment groups. In addition to descriptive summaries, a forest plot of the corresponding 95% CIs will be generated for each subgroup.

Mucosal S-IgA seroconversion rate (2-fold increase over baseline value or a 4-fold increase over the lower limit of assay detection [whenever the baseline value falls below the lower limit of assay detection]) with 95% CI will be calculated by treatment group at Day 29. A chi-square test will be used to compare seroconversion rates between treatment groups. Additional combinations of antibody response (WCE, PT, FHA, PRN, and any additional anti-pertussis antibodies) may also be tested.

Plots of the reverse cumulative distribution curves of each anti-pertussis mucosal antibody titre for mucosal S-IgA GMT will be generated for Day 29 by treatment group.

Further details will be provided in the SAP.

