3.2.2.3. Mucosal Secretory Immunogenicity

WCE, FHA, PRN, and any additional anti-pertussis mucosal antibodies identified during assay development using geometric mean concentration titre (GMT) and geometric mean fold rise (GMFR) unless otherwise stated.

NOTE: To also be tested separately in subjects who participate in the optional substudy as exploratory endpoints, to assess response following re-vaccination/attenuated challenge.

- BPZE1 induction of mucosal S-IgA against WCE compared with Boostrix at Day 29
- BPZE1 induction of mucosal S-IgA at Day 29 compared to baseline.
- BPZE1 and BPZE1 + Boostrix induction of mucosal S-IgA compared with baseline at Days 85 and 169/EOS (tested independently).
- BPZE1 + Boostrix induction of mucosal S-IgA compared with BPZE1 at Days 29 and 169/EOS (tested independently).
- BPZE1 and BPZE1 + Boostrix induction of mucosal S-IgA in covariate analysis by age, time since last aP vaccination (prior to study entry), or other baseline demographics at Day 29.

- BPZE1 and BPZE1 + Boostrix induction of mucosal S-IgA by baseline quantile at Day 29.
- Seroconversion rate (2-fold increase over baseline value or a 4-fold increase over the lower limit of assay detection [whenever the baseline value falls below the lower limit of assay detection]) for mucosal S-IgA at Day 29 by treatment group.
- Reverse cumulative distribution curves of each anti-pertussis mucosal antibodies S-IgA GMT at Day 29 by treatment group.

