For summary precision, mean and median will have one more decimal place than the reported value, SD will have two more decimal places than the reported value, minimum and maximum will have the same decimal place as the reported value. Percentages and 95% CIs will have one decimal place.

For immunogenicity analysis, it is assumed that the natural log of the data is normally distributed for the GMT/GMC/GMR, and GMFR.

GMT/GMC/GMR will be calculated as anti-logarithm of \sum (log-transformed titer/number of subjects with titer information). The 95% CI for GMT/GMC/GMR will be calculated as the anti-log transformation of upper and lower limits for a 2-sided 95% CI of the mean of the log-transformed values based on normal approximation.

For any antibody titer, if the result is reported as lower than the minimal limit of assay detection, a value equal to half of the minimal limit of assay detection will be imputed in the calculation. The minimal limit of assay detection for each of the antibody titers will be established following assay validation and prior to database lock.

GMFR will be calculated as anti-logarithm of \sum [log-transformed titer ratio of (Yi/Bi)/number of subjects with titer information], where Yi is the post-dose titer and Bi is the baseline titer for subject i. The same data summaries will be provided as GMT/GMC/GMR.

The mucosal and serum immunogenicity descriptive summaries (GMT/GMC/GMR and/or GMFR) will be provided by treatment group and by timepoint and across timepoints if applicable (all subjects), including a separate analysis after Day 85 for the open-label substudy. Analyses will include the GMT/GMC/GMR with 95% CIs and GMFRs with 95% CIs.

For seroconversion of mucosal S-IgA and serum IgA and IgG against WCE, PT, FHA, PRN, and any additional anti-pertussis antibodies identified during assay development, descriptive summaries including seroconversion rates and the 95% CIs will be provided by treatment group and by timepoint. Mucosal S-IgA will be normalized as [specific S-IgA]/[Total S-IgA (mg/mL)] and it will also be summarized using same method.

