Immunogenicity endpoints (seroconversion, GMT/GMC/GMR, and GMFR) will be summarized by baseline PRN negative and PRN positive status, by quantiles of each anti-pertussis antibody (WCE, PT, FHA, PRN, and any additional anti-pertussis antibodies) and by antibody type (eg, S-IgA, IgA, and IgG separately), by the 2 age groups (6 to 10 years and 11 to 17 years, inclusive) and across age groups. An additional age group of 10 to 17 years will be added for some analyses to be able to support a rationale for immunobridging to adults. A forest plot will be generated for subgroups.

The substudy analysis will assess immunogenicity endpoints at baseline and Days 85 and 113 (independently for substudy subjects) and relative to colonization status (colonized/non colonized) at either or both Day 92 and/or 99 following re-vaccination/attenuated challenge at Day 85.

All statistical tests will be 2 sided at 0.05 significance level.

If a substantial number of subjects receive a COVID-19 vaccine that is under an emergency use authorization only, then safety analysis may also assess any AEs that may be confounded by such concomitant vaccine administration during the study.

All data collected will be listed in data listings.

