8.3.1. Analyses of Secondary Mucosal Secretory Immunogenicity (S-IgA) Endpoints

Descriptive statistics (GMC/GMR [also known as GMT per protocol], GMFR, seroconversion) for mucosal S-IgA against WCE, PT, FHA, PRN, and any other anti-pertussis mucosal antibodies identified during assay development will be presented at each timepoint and by treatment groups. Mucosal S-IgA will also be normalized as [specific S-IgA]/[Total S-IgA (mg/mL)].

A non-inferiority hypothesis will be tested to demonstrate BPZE1 can adequately induce pertussis specific mucosal S-IgA responses at Day 29 against WCE (GMC/GMR and GMFR) compared with Boostrix. A two-sample t-test will be used to compare the natural log-transformed GMC/GMRs between BPZE1 and Boostrix groups. The non-inferiority margin is set at 2-fold decrease or -0.693 on natural log scale. Non-inferiority will be demonstrated if the lower limit of the 95% CI of group difference on natural log scale is greater than -0.693.

To test the hypothesis that BPZE1 can adequately induce pertussis-specific mucosal S-IgA responses at Day 29, Day 85, and Day 169/EOS against WCE, PRN, PT, and FHA compared with baseline by treatment group, separate paired t-tests will be used to compare the natural log-transformed GMC/GMR at Day 29, Day 85, Day 169/EOS with the natural log-transformed GMC/GMR at baseline within each of treatment groups. The corresponding 95% CIs will be calculated on the natural log scale, then both lower and upper limits will be exponentiated to obtain the 95% CIs on the original scale.

A non-inferiority hypothesis will be tested to demonstrate that BPZE1+Boostrix induction of mucosal S-IgA immunity is non-inferior to BPZE1 at Day 29 and Day 169/EOS. Separate ANCOVA models that include baseline S-IgA and treatment group as covariates will be used to compare the natural log-transformed GMCs/GMRs between BPZE1+Boostrix and BPZE1 groups. The non-inferiority objective will be demonstrated if the lower limit of the 95% CI of group difference on the natural log scale is greater than -0.693.

Subgroup analysis by age group (6-10 years and 11-17 years, inclusive, and 10 – 17 years [for requested analyses]), time since last aP vaccination prior to study entry (<median time, \geq median time), or other baseline demographics, and by baseline antibody level (by quantile) will be conducted to examine differential responses to induction of mucosal S-IgA at Day 29 for BPZE1

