and BPZE1 + Boostrix groups. In addition to descriptive summaries, a forest plot of the corresponding 95% CIs will be generated.

Mucosal S-IgA seroconversion rate is defined as 2-fold increase over baseline value or a 4-fold increase over the lower limit of assay detection (whenever the baseline value falls below the lower limit of assay detection). Mucosal S-IgA seroconversion rates will be calculated by BPZE1, BPZE1 + Boostrix, and Boostrix groups on Day 29. The 95% CI will be calculated by using Agresti-Coull method. The likelihood ratio chi-square test will be used to compare seroconversion rates among treatment groups. Additional combinations of antibody response (WCE, PT, FHA, PRN, and any additional anti-pertussis antibodies) may also be tested.

Graphics of the reverse cumulative distribution curves of each anti-pertussis mucosal antibody titer for mucosal S-IgA GMC/GMR will be generated for Day 29 by treatment group.

After natural logarithmic transformation, an ANCOVA model will be used to test the differences between treatment groups (BPZE1 vs Boostrix, BPZE1 + Boostrix vs Boostrix), with mucosal S-IgA against each of WCE, PT, PRN, FHA, and any additional anti-pertussis mucosal antibodies identified during assay development post vaccination at each of Days 29, 85, and 169/EOS as the dependent variable, vaccination as the treatment effect age, and baseline antibody value as covariates. The difference between treatment groups and the 95% CI for GMC/GMR on the natural log scale will be calculated.

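### The S-IgA analysis by baseline quantile leaves out the Boostrix arm, so regression to the mean in fold rise cannot be told apart from a real effect of baseline antibody level

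*SAP*

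**What the plan says.** - **Endpoint.** SAP 3.2.2.3 lists "BPZE1 and BPZE1 + Boostrix induction of mucosal S-IgA by baseline quantile at Day 29". The measures for this family of endpoints are stated once, as "using geometric mean concentration titre (GMT) and geometric mean fold rise (GMFR) unless otherwise stated".
- **Analysis.** SAP 8.3.1 plans a subgroup analysis "by baseline antibody level (by quantile) will be conducted to examine differential responses to induction of mucosal S-IgA at Day 29" for the two BPZE1-containing arms: "and BPZE1 + Boostrix groups. In addition to descriptive summaries, a forest plot of the corresponding 95% CIs will be generated". That sentence names no measure, test or interaction term.
- **Protocol.** Protocol 7.4.3.1 plans the same subgroup analysis "by baseline antibody level (by quantile) will be conducted for BPZE1, BPZE1 + Boostrix, and Boostrix treatment groups". SAP Section 1 says that the SAP governs where the two differ. SAP Section 11 does not list the loss of the Boostrix arm as a change.
- **Fold rise.** SAP Section 4 builds GMFR from the log of Yi/Bi, "where Yi is the post-dose titer and Bi is the baseline titer for subject i".
- **General summaries.** SAP Section 4 also says: "Immunogenicity endpoints (seroconversion, GMT/GMC/GMR, and GMFR) will be summarized by baseline PRN negative and PRN positive status, by quantiles of each anti-pertussis antibody". It adds a forest plot for subgroups. Neither is limited to the BPZE1 arms, and neither contrasts one arm with another.
- **ANCOVA.** The last paragraph of SAP 8.3.1 plans a model for each BPZE1-containing arm against Boostrix at Days 29, 85 and 169, with age and baseline as covariates and no treatment-by-baseline term.

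**The concern.** In a fold rise by baseline quantile, the same measured baseline value sorts the child into a subgroup and is the denominator of the outcome. A child whose baseline reading was low partly by chance lands in the lowest quantile and tends to read higher on Day 29. The reverse holds at the top. A falling gradient in GMFR therefore appears without any true dependence of the vaccine effect on baseline.

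At stake is the reading of a stated secondary objective. A forest plot confined to the BPZE1 arms invites the conclusion that children with low baseline S-IgA respond better. The Boostrix arm carries the same regression to the mean and would show how much of the gradient is artefact, but SAP 8.3.1 leaves it out.

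**Working it through.** **1. The plan's own figure.** The documents give no figure for the quantile analysis. The nearest is the power for the primary paired t-test (SAP 4.1.1): N = 108, effect size 0.35, two-sided 0.05. With a noncentral t on 107 degrees of freedom and noncentrality 0.35 × √108 = 3.64, power is 95.0%, and 0.95 × 0.95 = 0.90. Both stated figures reproduce.

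**2. Inputs.**
- From the documents: 108 evaluable per arm.
- Assumed: quartiles (108 / 4 = 27 each), because the SAP does not say which quantiles; ln baseline and ln Day 29 bivariate normal with equal variances and correlation ρ; no values below the detection limit.
- Not in the documents: ρ and the SD of ln S-IgA. SD 1.0 is used. The range 0.82 to 1.44 is borrowed from the serum IgG SDs in SAP Table 4-2 for illustration only.

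**3. Formula.** Give every child the same true log rise. The slope of ln fold rise on observed baseline is then −(1 − ρ). The mean of the top quarter of a normal distribution is 1.271 SD, so the lowest-to-highest gap in ln GMFR is 2 × 1.271 × (1 − ρ) × SD. The SD of the change is SD × √(2(1 − ρ)), so the gap in those units is 1.798 × √(1 − ρ).

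**4. Results** (3,000 simulated trials per row, no effect modification). Non-overlap refers to the 95% intervals of the lowest and highest quartile GMFR within one BPZE1 arm. The last column is the 5%-level rejection rate of an arm-by-baseline interaction on ln Day 29 S-IgA, 108 versus 108, with Boostrix as reference.

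| ρ | Gap, in SDs of the change | Lowest:highest GMFR ratio, SD 1.0 | Same, SD 0.82 to 1.44 | Intervals do not overlap | Interaction rejects |
|---|---|---|---|---|---|
| 0.3 | 1.50 | 5.9 | 4.3 to 12.9 | >99.9% | 5.3% |
| 0.5 | 1.27 | 3.6 | 2.8 to 6.2 | 98% | 5.8% |
| 0.7 | 0.98 | 2.1 | 1.9 to 3.0 | 82% | 5.5% |
| 0.8 | 0.80 | 1.7 | 1.5 to 2.1 | 56% | 5.4% |
| 0.9 | 0.57 | 1.3 | 1.2 to 1.4 | 21% to 22% (two runs) | 5.0% |
| 0.95 | 0.40 | 1.1 | 1.1 to 1.2 | 9% | 4.9% |

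The gap in the second column exceeds the design effect size of 0.35 in every row. In this model the non-overlap rates depend on ρ alone: a different SD rescales every interval, and a uniform rise shifts them all equally.

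**5. With a uniform vaccine effect.** At ρ = 0.7, SD 1.0 and a true 3-fold rise for everyone, the quartile GMFRs are 3 × exp(±1.271 × 0.3) = 4.39 and 2.05 (simulated: 4.36 and 2.05). The false gradient stays, but both intervals lie above 1.

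**6. Day 29 GMT instead of GMFR.** Its slope on baseline is +ρ. With SD 1.0 and no vaccine effect, simulated Day 29 GMT is 3.5, 5.8 and 9.7 times higher in the highest quartile than in the lowest at ρ = 0.5, 0.7 and 0.9. The two planned measures therefore show opposite gradients in the same null data.

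**7. Seroconversion.** At ρ = 0.5, SD 1.0 and no vaccine effect, a plain 2-fold rule gives 47% in the lowest quartile and 7% in the highest. SAP 8.3.1 instead requires 4-fold over the detection limit when baseline is below it. If 10%, 25% or 40% of baselines are below the limit (assumed), the lowest quartile drops to 29%, 8% or 2%, against 7%.

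**The case against.** The strongest reply is that nothing is tested. The objective is to assess, the output is descriptive, and no document sets a decision rule or a reference line for the forest plot. SAP Section 4 can also show quantile summaries and a subgroup plot with Boostrix included, so it would go too far to infer that the plan never displays that arm. All this stands and limits the weight of the point. But the stated purpose in 8.3.1 is to examine differential responses, and neither section plans the between-arm contrast that could do so.

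Three stronger readings are tempting and not supported:
- **That the trial will almost surely report a response at low baseline and none, or a loss, at high baseline.** This needs a low ρ together with little or no vaccine effect. Neither is established, and step 5 shows a counterexample.
- **That seroconversion carries the same artefact.** Step 7 shows that the below-detection rule can remove or reverse its gradient, so no general claim can be made.
- **That the serum analysis in SAP 8.3.2 needs the same change.** It already keeps Boostrix, and its endpoint is assessed independently in each treatment group. Boostrix itself drives the serum response, so a contrast with Boostrix would cancel part of what that objective asks about.

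The 8.3.1 sentence also does not name fold rise; that GMFR will be used rests on the endpoint family and on SAP Section 4. Relying on Day 29 GMT would not help (step 6).

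**Conclusion.** The point holds for the S-IgA baseline-quantile analysis in SAP 8.3.1. As written, it cannot separate a true effect of baseline level from regression to the mean in GMFR. Under the normal, equal-variance model with quartiles, the artefact is strong at ρ of about 0.7 or below and modest at 0.9 or above. The false gradient persists under a uniform vaccine effect, though the highest quartile need not show a GMFR at or below 1. A treatment-by-baseline interaction against Boostrix rejects in 4.9% to 5.8% of null trials across the whole range, close to nominal. Using Boostrix as the reference is reasonable because, according to Protocol 1.1, it did not induce S-IgA in the adult Phase 2b study. The matter is confined to one descriptive secondary analysis, but it is worth correcting.

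**What to change.** In SAP 8.3.1:
1. Restore the Boostrix arm to the S-IgA baseline-quantile analysis, as in Protocol 7.4.3.1.
2. Add a treatment-by-baseline term to the Day 29 ANCOVA against Boostrix that is already planned there.
3. Have the forest plot show the BPZE1/Boostrix and BPZE1 + Boostrix/Boostrix ratios within each baseline quantile.
4. Label within-arm GMFR and seroconversion by quantile as descriptive and subject to regression to the mean.

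Make no between-arm change to the serum analysis in 8.3.2.

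The cost is SAP wording and one model term; no new data are needed. The downside is precision: with equal spread, a ratio of two groups of 27 has √(1/27 + 1/27) / √(1/27) = √2 times the standard error, on the log scale, of one group of 27, and the interaction will be estimated loosely.

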MAAE	medically attended adverse event
MAD	mucosal atomization device
MedDRA	Medical Dictionary for Regulatory Activities
OTC	over the counter
PBMC	peripheral blood mononuclear cell
PCR	polymerase chain reaction
PRN	pertactin
PT	pertussis toxin
PT	preferred term
RRR	reduction of relative risk
SAE	serious adverse event
SAP	statistical analysis plan
S-IgA	secretory immunoglobulin A
SMC	safety monitoring committee
SOC	system organ class

SUSAR	suspected unexpected serious adverse reaction
Tdap	tetanus toxoid, reduced diphtheria toxoid, and acellular pertussis
WCE	whole cell extract
wP	whole cell pertussis

1. Introduction

This statistical analysis plan (SAP) describes the analyses and data presentations for ILiAD's protocol IB-201P "A Phase 2b, Multi-Center, Placebo-Controlled, Randomized Study of BPZE1 Intranasal Pertussis Vaccine in Healthy School-Age Children to Assess the Immunological Response and Safety Profile of a Single Dose BPZE1 With and Without Co-Administration of Tetanus, Diphtheria, and Acellular Pertussis (Boostrix™)" which was issued on 03FEB2021 (amended 02APR2021, 09JUN2021, 07JUL2021, 16AUG2021, 30MAY2022, and 30MAR2023 (still in use in countries outside Costa Rica), 10OCT2023 (applicable in Costa Rica only)). It contains definitions of analysis populations, derived variables, and statistical methods for the analysis of immunogenicity, colonization (substudy only) and safety.

These analyses include one (1) interim analysis and one final analysis. The purpose of the SAP is to ensure the credibility of the study findings by pre-specifying the statistical approaches to the analysis of study data prior to database lock and any data analysis for the interim/final analyses. This SAP is to be interpreted in conjunction with the protocol. Should the SAP and protocol be inconsistent with respect to the planned analyses, the language of the SAP is governing. This SAP will be finalized and signed prior to the clinical database lock for the interim analyses. If the final clinical study report (CSR) contains changes to any planned statistical analyses, the justification for any such differences will be fully documented in the CSR. All statistical analyses detailed in this SAP will be conducted using SAS® Version 9.4 or higher.

2. Objectives

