of serum IgA and IgG is non-inferior to Boostrix at Day 85 and Day 169/EOS. An ANCOVA model that includes baseline IgA or IgG and treatment group as covariates will be used to compare the natural log-transformed GMCs at Day 85 and Day 169/EOS between either BPZE1 or BPZE1+Boostrix and Boostrix groups. The non-inferiority margin is set at a 2-fold decrease or -0.693 on natural log scale. Non-inferiority will be demonstrated if the lower limit of the 95% CI of group difference on natural log scale is greater than -0.693.

Subgroup analysis by age group (6-10 years and 11-17 years, inclusive, and 10 – 17 years [for requested analyses]), time since last aP vaccination prior to study entry (<median time, \geq median time), or other baseline demographics, and by baseline antibody level (by quantile) will be conducted to examine differential responses to induction of serum immunity (IgA, IgG) at Day 29 by treatment group (BPZE1, BPZE1+Boostrix, and Boostrix). In addition to descriptive summaries, a forest plot of the corresponding 95% CIs will be generated for each subgroup.

To compare BPZE1 and BPZE1 + Boostrix induction of measurable functional antibody (subset of subjects) with Boostrix at Day 29, separate two-sample t-tests will be used to compare between treatment group differences in natural log-transformed GMC at Day 29. The corresponding 95% CIs by treatment group will be calculated on the natural log scale, then both lower and upper limits will be exponentiated to get the 95% CIs on the original scale.

Seroconversion rates with 95% CIs for IgA and IgG will be calculated at Days 29 and 85 by treatment group and day. The 95% CI will be calculated by using Agresti-Coull method. The likelihood ratio chi-square test will be used to compare seroconversion rate between treatment groups. Additional combinations of antibody response (WCE, PT, FHA, PRN, and any additional anti-pertussis antibodies) may also be tested.

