The number and proportion of subjects with a $\geq 2x$ increase from baseline in SBA bactericidal titer (50% killing titer) will be summarized by treatment group, by timepoint and by strain. The 95% CIs for each treatment group will be computed using the Agresti-Coull method and the 95% CIs for the difference in proportions between groups (BPZE1 vs Boostrix, BPZE1 + Boostrix vs Boostrix) will be computed using Agresti Caffo method. A chi-square test will be performed to compare the proportion of subjects between groups (BPZE1 vs Boostrix, BPZE1 + Boostrix vs Boostrix) with a $\geq 2x$ increase in SBA bactericidal titer and two-sided p-value will be provided.

Reverse cumulative distribution curves will be provided for SBA (PRN+ and PRN-) at baseline, Day 29 and Day 113.

9. Safety Analysis

Unless otherwise specified, safety analysis will be performed based on the Safety Analysis Set. Safety analysis for safety lead-in cohort will be performed based on the Safety Lead-in Analysis Set. All summaries and analyses will be presented by treatment groups (BPZE1, BPZE1 + Boostrix, Boostrix), age group, and overall for first study vaccination and following re-vaccination/attenuated challenge (substudy) separately.

9.1.Solicited Adverse Events

The number and percentage of subjects with any solicited AEs (local, nasal/respiratory, and systemic reactogenicity events) through 7 days following first study vaccination with any

combination of pertussis-containing vaccines (BPZE1, BPZE1 + Boostrix, Boostrix) will be calculated by treatment group, age group and overall, and by timepoint.

Solicited reactogenicity events occurring from the time of study vaccination on Day 1 for 7 consecutive days starting the day following study vaccination, including local, nasal/respiratory reactions and systemic reactogenicity, will be summarized as presenting both the number and frequency, categorized by the severity grades according to respective reactogenicity grades (Table 9-1-1, Table 9-1-2, and Table 9-1-3).

Additionally, solicited AEs will be analyzed by determining the maximum severity through 7 days following study vaccination on Day 1 to summarize the frequency and percentage of subjects reporting each local, nasal/respiratory, or systemic event.

Redness measurements, swelling measurements, and oral temperature if subjects have fever for 7 days following vaccination will be summarized using descriptive statistics.

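### Seroconversion has no named pairwise contrast and no interval for a difference; the S-IgA test is a three-arm likelihood-ratio chi-square that cannot say which arm differs (minor, cheap to improve)

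*SAP*

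**What the plan says.** **Mucosal S-IgA, Day 29 (SAP 8.3.1).** "Mucosal S-IgA seroconversion rates will be calculated by BPZE1, BPZE1 + Boostrix, and Boostrix groups on Day 29". The interval is for each arm's rate: "The 95% CI will be calculated by using Agresti-Coull method". The test is "The likelihood ratio chi-square test will be used to compare seroconversion rates among treatment groups". No pair is named and no interval for a difference is planned.

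**Serum IgA and IgG, Days 29 and 85 (SAP 8.3.2).** "The likelihood ratio chi-square test will be used to compare seroconversion rate between treatment groups". The Ward-criteria paragraph in the same section repeats the test. Neither names pairs.

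**Protocol 7.4.3.1.** "A chi-square test will be used to compare seroconversion rates between treatment groups", with the type of chi-square left open. If the documents differ, SAP section 1 settles it: "Should the SAP and protocol be inconsistent with respect to the planned analyses, the language of the SAP is governing". SAP section 4 sets the level: "All statistical tests will be 2 sided at 0.05 significance level".

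**Where the SAP does name pairs.** For the other fold-rise responder endpoint, a two-fold rise in bactericidal titre, SAP 8.4.3 says that the interval for the "difference in proportions between groups (BPZE1 vs Boostrix, BPZE1 + Boostrix vs Boostrix) will be computed using Agresti Caffo method". The S-IgA titre ANCOVA at the end of SAP 8.3.1 names the same two pairs.

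**The concern.** The design asks two between-arm questions: does BPZE1, alone or with Boostrix, produce a response that Boostrix does not, and does giving the two together weaken either? Both concern pairs of arms. A two-degree-of-freedom test across three arms asks only whether the rates are not all equal. A small p-value for S-IgA seroconversion would fit a response kept on co-administration and equally one lost on co-administration.

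The statistic raises a second, separate issue. The likelihood-ratio chi-square follows its reference distribution less well than Pearson's when few children seroconvert, or nearly all do. Low S-IgA rates are conceivable for PT: protocol 1.1 reports adult S-IgA induction for WCE, FHA and PRN and does not list PT, while SAP 8.3.1 analyses S-IgA to PT. The documents give no rate for it.

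At stake is how a secondary endpoint can be read, not whether the trial succeeds.

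**Working it through.** **Inputs.** Arms: A = BPZE1, B = BPZE1 + Boostrix, C = Boostrix. Allocation is 1:1:1 with 120 per arm and 10% drop-out (SAP 4.1), so n = 120 × 0.9 = 108. Two-sided level 0.05. The documents state no seroconversion rates, so **every rate below is an assumption**.

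**1. The plan's own figure.** There is none for seroconversion. The nearest one that fixes n and the level is the primary power in SAP 4.1.1. Paired t-test: noncentrality 0.35 × √108 = 3.637, critical value 1.982 on 107 df, power 0.950; both comparisons 0.950² = 0.902. The stated 95% and 90% reproduce.

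**2. What the three-arm test sees.** G² = 2 Σ O ln(O/E) over the six cells, with critical value 5.99 on 2 df. Two example tables with 108 per arm:
- Seroconverters 43, 43, 11 (about 40/40/10%). E = 97/3 = 32.33 converters and 75.67 non-converters per arm. G² = 2[2·43 ln(43/32.33) + 11 ln(11/32.33) + 2·65 ln(65/75.67) + 97 ln(97/75.67)] = 34.0.
- Seroconverters 43, 11, 11 (about 40/10/10%). E = 65/3 = 21.67 and 86.33. G² = 2[43 ln(43/21.67) + 2·11 ln(11/21.67) + 65 ln(65/86.33) + 2·97 ln(97/86.33)] = 37.4.

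Both lie far above 5.99. Nothing in the statistic separates response kept from response lost.

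**3. Rejection over repeated trials.** Exact sum of the binomial probabilities of all tables with G² above the critical value, likelihood-ratio statistic throughout:

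| Assumed A/B/C | Three-arm test | A v B | A v C | B v C |
|---|---|---|---|---|
| 40/40/10% | about 100% | 4.9% | about 100% | about 100% |
| 40/10/10% | about 100% | about 100% | about 100% | 5.3% |
| 80/90/90% | 58% | 55% | 55% | 5.3% |
| 30/30/20% | 40% | 5.1% | 40% | 40% |

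The first two rows match on the planned test and differ only in the pairs.

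**4. Actual error at nominal 5%, same rate in every arm compared.** The same exact sum:

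| Common rate | Three-arm LR | Three-arm Pearson | Pairwise LR | Pairwise Pearson |
|---|---|---|---|---|
| 0.5% | 2.0% | 1.8% | 2.0% | 0.3% |
| 2% | 7.8% | 4.0% | 9.4% | 4.2% |
| 3% | 7.4% | 4.4% | 8.1% | 4.4% |
| 5% | 6.1% | 4.7% | 6.3% | 4.5% |
| 10% | 5.4% | 4.8% | 5.3% | 5.3% |
| 50% | 5.2% | 5.2% | 4.8% | 4.8% |

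The three-arm likelihood-ratio maximum is 7.9%, near a 2.2% rate. It exceeds 5.5% only for common rates of about 1.2% to 7.6%, and the mirror range at the top.

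One pair shows why. With 0 v 3 seroconverters of 108, E = 1.5 and 106.5. G² = 2[3 ln 2 + 108 ln(108/106.5) + 105 ln(105/106.5)] = 4.20, p = 0.040. Pearson X² = 2(1.5²/1.5) + 2(1.5²/106.5) = 3.04, p = 0.081. So naming pairs while keeping the likelihood-ratio statistic would not cure this.

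**5. The alternative already in the SAP.** Agresti-Caffo: p̃ = (x+1)/(n+2), interval d̃ ± 1.96 √{[p̃₁(1−p̃₁) + p̃₂(1−p̃₂)]/(n+2)}. For 43 v 11: 44/110 − 12/110 = 0.291, interval 0.182 to 0.399. For 11 v 11: 0 ± 0.082. The second example table would thus show B below A and no evident gap between B and C. Over repeated trials the interval excludes zero 99.7% of the time for 50% v 20% and 96% for 30% v 10%. Under equal rates it does so 0.6% of the time at 2%, 3.0% at 5% and 4.8% at 50%.

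**The case against.** The strongest case is that the questions that matter are tested elsewhere, in named pairs. That stands. Interference with Boostrix antigens is tested in SAP 8.2, BPZE1 + Boostrix against Boostrix, by ANCOVA on PT, FHA and PRN titres and by Agresti-Caffo on diphtheria and tetanus proportions. SAP 8.3.1 tests BPZE1 + Boostrix against BPZE1 for non-inferiority on S-IgA titres, and compares each BPZE1 arm with Boostrix by ANCOVA. A reader might infer that interference goes untested; the documents do not support that.

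A reader might also take all seroconversion tests to be three-arm tests. That is firm only for S-IgA, where the text says *among*. SAP 8.3.2, its Ward paragraph and protocol 7.4.3.1 say *between*, and SAP 8.4.1 uses similar wording for colonization before listing four pairwise relative risks. For serum the defect is that the pairs are unnamed.

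Nor must the serum test reject because the BPZE1-only arm receives saline by injection. Protocol 1.1 reports that BPZE1 induced serum IgG to PT, FHA and PRN in adults, and 80/90/90% gives 58%, not certainty. For S-IgA, rejection driven by the arm without BPZE1 is a true BPZE1 effect, not an artefact.

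Finally, seroconversion is an endpoint to be assessed, with no margin or success criterion, and the per-arm Agresti-Coull intervals would make a 40/10/10% pattern visible. That lowers the stakes. It does not supply a pre-specified contrast, which SAP 8.4.3 does supply for bactericidal responders.

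**Conclusion.** The point holds as a minor one. The S-IgA seroconversion p-value cannot say which arm differs, the serum and Ward comparisons leave their pairs open, and no interval for a difference is planned in either section. How often the three-arm test rejects depends on rates that the documents do not give: from 40% to about 100% in the scenarios tried.

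The excess error of the likelihood-ratio statistic is real but narrow. It needs the compared arms to share a rate of about 1-8%, or the mirror range, and it is close to nominal from about 10%. A reader might infer general inflation at low rates; at a 0.5% common rate the test is conservative (2.0%). Nor can the inflation act together with the large-gap problem on the same antigen, because one needs equal rates and the other unequal ones.

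The primary, key secondary and titre-based secondary conclusions are unaffected.

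**What to change.** In SAP 8.3.1 and 8.3.2, including the Ward paragraph:
- Name BPZE1 v Boostrix and BPZE1 + Boostrix v Boostrix. For S-IgA add BPZE1 + Boostrix v BPZE1, matching the co-administration objective in SAP 2.2.3.
- Report each difference in proportions with an Agresti-Caffo 95% interval, as in SAP 8.4.3. Keep the per-arm Agresti-Coull intervals.
- Replace the likelihood-ratio test with Pearson's chi-square, or an exact test under a stated rule for sparse counts. The Agresti-Caffo interval is more conservative than Pearson at low rates (0.6% against 4.2% at 2%), so say that the interval carries the interpretation if the two disagree.
- State that these comparisons are secondary and unadjusted.

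**Cost.** Wording and extra table columns; the Agresti-Caffo method is already needed for SAP 8.2 and 8.4.3. The downside is the number of tests. With four antigens: S-IgA 4 × 3 = 12; serum 4 antigens × 2 isotypes × 2 days × 2 pairs = 32; Ward 2 isotypes × 2 pairs = 4. That makes 48 unadjusted comparisons before any added antigens or normalised S-IgA versions, which is why the label is needed. Fixing the pairs before unblinding also removes any later choice among them.
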